### **Sensitivity analysis**

In the ITT dataset, we will perform a sensitivity analysis by fitting a multivariable logistic regression model of the primary outcome with covariate adjustment. Prognostic or risk factors of postoperative delirium shown in previous literature, and baseline and perioperative variables that differed between groups ( $p < 0.10$ ) together with the intervention factor (administration of dexmedetomidine or not) will be entered into the regression model. As the incidence of delirium is not a rare event, the odds ratio (OR) estimate from the logistic regression analysis will possibly overestimate the relative risk (RR) – our measure of effect size in this study, we will convert the OR into RR using the Zhang and Yu method (Zhang J, Yu KF. What's the relative risk? A method of correcting the odds ratio in cohort studies of common outcomes. *Jama* 1998;280:1690-1)

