### **6.4 Anesthetic care guided by EEG monitoring**

- 1) The monitor screen in the control arm is covered and blinded to the anesthesiologist;
- 2) The monitor in the intervention arm is used by the anesthesiologist to adjust the anesthetic care.
- 3) The goal in the intervention arm is to maintain SEF 10-15 throughout surgery. Avoid burst-suppression.
- 4) In the intervention arm, the anesthesia induction is achieved via propofol pump infusion (slow and controlled). The goal is to avoid burst-suppression and maintain SEF > 10 throughout anesthesia induction.
- 5) The anesthesia maintenance is achieved via the protocol detailed below (6.5). The SedLine-guided intervention protocol is detailed in the **Supplemental remark 1. SedLine-Guided Intervention Flow Chart**.

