### **6.5 Anesthesia protocol for both intervention and control group**

- 1) During the study period (from preop to postop day 5), anticholinergics such as scopolamine are strictly prohibited; atropine or glycopyrrolate can only be used for treatment of bradycardia; the use of midazolam for anxiolysis is allowed but not encouraged;
- 2) In both arms, the anesthesia induction is per standard care using agents of lidocaine, propofol, sufentanyl and muscle relaxant. The administration of propofol in the intervention arm is via pump infusion and guided by SedLine.
- 3) The anesthesia is maintained using propofol infusion (0-200 mcg/kg/min) and remifentanyl infusion (0.05-0.2 mcg/min/kg). Sufentanyl and muscle relaxant boluses can be used during surgery.
- 4) The anesthetic adjustment in the control arm is per the conventional practice (EEG monitored but blinded to anesthesia team) and in the intervention arm per the **Supplemental remark 1. SedLine-Guided Intervention Flow Chart**.

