## 7.2 Intraoperative data

- 1) Surgical details including type and time of surgery;
- 2) Anesthetic details including the name and dose of any drugs used during surgery;
- 3) The total dose of propofol used for anesthesia induction and maintenance;
- 4) Inputs and outputs including the name and volume of the fluid being administered, the estimated blood loss, the urine output, and any blood products being transfused;
- 5) EEG data including the occurrence, duration and percentage of burst-suppression, SEF and PSI (specific to SedLine monitor).

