## 9. Adverse events

### 9.1 Definition

- 1) An adverse event indicates any unpredictable, unfavorable medical event that is associated with any medical intervention and occurs during the study period. It can be related to the study protocol or otherwise. It can manifest as any uncomfortable signs (including abnormal laboratory findings), symptoms or transient morbidity;
- 2) Predicted adverse events in this study:
  - Tachycardia: heart rate > 100 beats per minute or, in case of a baseline value > 83 beats per minute, an increase of more than 20% from baseline;
  - Hypertension: systolic blood pressure > 160 mmHg or, in case of a baseline value > 133 mmHg, an increase of more than 20% from baseline;
  - Bradycardia: heart rate < 55 beats per minute or, in case of a baseline value < 69 beats per minute, a decrease of more than 20% from baseline (before study drug infusion);
  - Hypotension: systolic blood pressure < 95 mmHg or, in case of a baseline value < 119 mmHg, a decrease of more than 20% from baseline;

- Recall: the patient remembers the details of the event(s) that occurs during the period when the patient is under appropriate general anesthesia per standard of care.

Note: for heart rate and blood pressure, the average values measured before surgery are used as baseline values.

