### **10.3 Recording and reporting**

- 1) In case of any severe adverse event, apart from active treatment and record as above, the principal investigator and the Ethics Committee will be informed within 24 hours in written report;
- 2) In case of study drug related death, immediately stop the clinical trial, report the event to the Ethics Committee as soon as possible, record in detail and carefully preserve the related documents;
- 3) Any severe adverse event must be followed up until it is completely resolved or the therapy is terminated.

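### The only covariate-adjusted model of the primary outcome names dexmedetomidine, not randomised SedLine guidance, as the treatment term, and it admits perioperative variables that the intervention is meant to change

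*Combined protocol and SAP*

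**What the plan says.** Section 13.5 (Sensitivity analysis) plans one multivariable logistic regression of the primary outcome, with the odds ratio converted to a relative risk by the Zhang-Yu method. On the treatment term it says that "the intervention factor (administration of dexmedetomidine or not) will be entered into the regression model". The covariates are risk factors for delirium from the literature, not listed, together with "baseline and perioperative variables that differed between groups" at p < 0.10.

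The trial randomises something else. Under section 6.4 the monitor is visible and used in one arm and covered in the other. Section 13.3 names the arms as SedLine-guided care and usual care. Dexmedetomidine is not in the anesthesia protocol of section 6.5. Elsewhere in the readable text it appears only as a tick-box among the maintenance drugs on the case report form.

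On what the intervention acts upon, section 6.4 says: "The goal in the intervention arm is to maintain SEF 10-15 throughout surgery. Avoid burst-suppression". Section 6.5 adds: "The administration of propofol in the intervention arm is via pump infusion and guided by SedLine". Section 7.2 lists among the intraoperative data "EEG data including the occurrence, duration and percentage of burst-suppression, SEF and PSI" and "The total dose of propofol used for anesthesia induction and maintenance".

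Section 13.4 describes the p-value screen for baseline variables only. Section 13.5 is wider.

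**The concern.** There are two separate faults.

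**Treatment term.** A model whose treatment variable is dexmedetomidine use does not estimate the effect of SedLine guidance. The wording looks like carry-over from a drug trial. Section 9.1 has "before study drug infusion" and section 10.3 has "In case of study drug related death", although this trial has no study drug. That origin is an inference, and nothing in the readable text corrects the term.

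**Covariates on the causal pathway.** Suppose the term is corrected. If guidance works as intended, the arms will differ on SEF, burst suppression and probably propofol dose. A difference between arms is exactly what the p < 0.10 rule selects on, so the rule tends to admit the variables through which the intervention acts. The literature clause is a second route: section 1 names anesthetic dosing as a modifiable risk factor for delirium and cites burst suppression as associated with it.

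The stake is interpretation. This is the only adjusted check on the primary result. A true benefit could shrink or vanish in it and be read as a lack of robustness.

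**Working it through.** **1. The plan's own figure.** Section 4.2 gives a 14% control risk, a one-third reduction, two-sided 0.05 and 80% power. The intervention risk is 0.14 × 2/3 = 0.0933 and the mean risk is 0.1167. With pooled variance and no continuity correction:

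n = [1.96·√(2 × 0.1167 × 0.8833) + 0.8416·√(0.14 × 0.86 + 0.0933 × 0.9067)]² / 0.0467² = 741.7, so 742 per arm, as stated.

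Expected events: 742 × (0.14 + 0.0933) ≈ 173. The target odds ratio is (0.0933/0.9067)/(0.14/0.86) = 0.632.

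**2. The model read literally.** Assume dexmedetomidine is used in 10% to 50% of patients, independently of arm, and has no effect. Its odds ratio is then about 1 (0.97 to 1.00 in simulation). It is significant in about 4% to 5% of trials, even though the full SedLine effect is present.

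**3. Does a shifted variable pass the screen?** In SD units the standard error of a difference in means is √(2/742) = 0.0519, so p < 0.10 needs an observed difference of 1.645 × 0.0519 = 0.085 SD.

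| True shift (SD) | Probability of entering the model |
|---|---|
| 0.05 | 0.252 |
| 0.10 | 0.611 |
| 0.15 | 0.893 |
| 0.20 | 0.986 |

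Moderate shifts nearly always enter; small ones often do not.

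**4. What adjustment does to the effect.** Assumptions, not document figures: one pathway variable M, normal with SD 1, lowered by d = 0.3, 0.5 or 0.8 SD in the intervention arm, and carrying 25%, 50% or 100% of the log-odds effect. The outcome model is logit P = b0 + bA·A + bM·M. In every scenario b0 and the total effect are solved so that the marginal risks are exactly 0.14 and 0.0933. The crude relative risk is therefore always 0.667.

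The conversion is RR = OR / (1 − P0 + P0·OR) with P0 = 0.14. Check: 0.632 / (0.86 + 0.14 × 0.632) = 0.667. Example at d = 0.5 and a 50% share: bA = −0.234, OR = 0.791, RR = 0.791 / (0.86 + 0.14 × 0.791) = 0.815.

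| Share through M | Adjusted RR (d = 0.3 / 0.5 / 0.8) | Adjusted term significant | Adjusted term non-significant when the unadjusted test is significant |
|---|---|---|---|
| 0% | 0.667 at every d | 76% (d = 0.5) | 3% / 6% / 9% |
| 25% | 0.736 / 0.738 / 0.739 | 51–55% | 32% / 35% / 36% |
| 50% | 0.806 / 0.815 / 0.817 | 26–29% | 64% / 65% / 68% |
| 100% | 1.00 at every d | about 5% | 97% at every d |

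The last column comes from 2,000 simulated trials per cell; the unadjusted test was significant in 78% to 81% of them. A repeat with another random seed agreed to within 3 percentage points. At 100% the adjusted term has no effect left to detect, so it is significant only at about the nominal 5% rate.

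**5. How demanding is the extreme row?** Full mediation at d = 0.3 needs M to have an odds ratio of 11.7 per SD on delirium, which is extreme. At d = 0.8 it needs 1.8.

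**The case against.** Five points can be made for the plan.

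- *The treatment term is an editorial slip.* Section 13.5 speaks of differences between groups and of the relative risk as the trial's effect measure, so a statistician would probably enter the arm. That is likely, but the parenthesis defines the term explicitly and would have to be overruled to do it.
- *Not all of the file can be read.* The flow chart in Supplemental remark 1 is not shown. It might mention dexmedetomidine, but that would not make it the randomised factor.
- *Section 13.4 limits the screen to baseline variables, and section 13.5 names no EEG or propofol covariate.* This stands in part: the two sections disagree, and entry of pathway variables is permitted rather than prescribed. Section 13.4 does not cancel the wider wording, and nothing excludes post-randomisation variables. A perioperative variable off the pathway, which blood loss or transfusion might be, would not cause this bias.
- *The size rests on assumptions.* This stands. At a 10% share the adjusted relative risk is only 0.69 to 0.70. Adding a prognostic covariate with log-odds SD 1.0 (also an assumption) gives 0.71 at a 25% share and 0.79 to 0.80 at 50%. The plan also sets no significance criterion for this model, so the non-significance rates show how it might be read; they do not describe a decision rule.
- *The p < 0.10 screen on baseline variables does not cause this bias.* True. The case for replacing it is that a fixed list closes both routes by which pathway variables can enter.

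**Conclusion.** Both faults hold on the text. As written, the model's treatment term is not the randomised factor, so it does not estimate the trial's effect. With the term corrected, the covariate rule still lets in what the intervention is designed to change. The planned relative risk of 0.667 would then appear as about 0.74, 0.81 to 0.82 or 1.00 at mediated shares of 25%, 50% or 100%, and there is no attenuation at a share of zero. Losing the whole effect requires complete mediation. The shares and shifts are assumed; the risks and sample size are the plan's.

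The damage is confined to this sensitivity analysis. The primary chi-square comparison and relative risk in section 13.5, the alpha level and the sample size all stand. It should be fixed, because it is the only adjusted support for the primary result and the repair is cheap.

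**What to change.** In section 13.5 (Sensitivity analysis):

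1. Define the treatment term as SedLine-guided versus usual care, as randomised.
2. Remove perioperative variables from the covariate rule. Replace the p < 0.10 screen and the open reference to the literature with a short, fixed list of baseline prognostic covariates already collected, for example age, preoperative MMSE, ASA class and Charlson score.
3. Amend section 13.4 to match, since it ties its baseline p-values to this model.
4. If adjustment for propofol dose, SEF, burst suppression or PSI is of interest, describe it as a separate exploratory mediation analysis.
5. In the same edit, align the dataset name: section 13.5 says ITT, while section 13.3 defines only a modified ITT population.

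Optional and minor: report a standardised marginal relative risk in place of the Zhang-Yu conversion. That conversion gives 0.652 against a true 0.667 when the covariates have a log-odds SD of 0.7 (assumed).

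The cost is wording in the analysis plan, with no new data. The one small downside is that a chance imbalance in an unlisted baseline variable would not be adjusted for.

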### **4.2 Sample size calculation**

The incidence of postoperative delirium is about 14% in elderly patients who underwent laparoscopic surgery for colorectal cancer [Tei et al., 2016]. We assume that the incidence of postoperative delirium will be reduced by 1/3 in patients receiving EEG-guided care [Chan et al., 2013]. With a two-sided significance and power set at 0.05 and 80%, respectively, the sample size required to detect the reduction is 742 patients per group. Taking into account a loss-to-follow-up rate of about 5%, we plan to enroll 780 patients in each group.

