## **5. Randomization and blinding**

### **5.1 Randomization**

- 1) A biostatistician who does not participate in data management and statistical analysis will generate random numbers in a 1:1 ratio;
- 2) The results of randomization will be sealed in sequentially numbered envelopes, stored at the site of investigation, and managed by the study coordinator.
- 3) Timing of randomization of individual patient: 30-60 mins before surgery

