#### **13.5 Effectiveness evaluation**

##### **Evaluation of primary endpoint**

The incidence of postoperative delirium within 5 days after surgery will be calculated. Comparison between groups will be performed with chi-square or Fisher's exact test. The relative risk and the corresponding 95% confidence interval (CI) will be calculated to measure the magnitude of difference in risk of having postoperative delirium between groups.

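### The Zhang-Yu step in the sensitivity analysis converts a covariate-adjusted odds ratio, so the adjusted relative risk is not on the marginal scale of the primary relative risk and, with prognostic baseline covariates, moves away from 1

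*Combined protocol and SAP*

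**What the plan says.** Section 13.5, Evaluation of primary endpoint, compares incidence by chi-square or Fisher's exact test, without covariates, and adds: "The relative risk and the corresponding 95% confidence interval (CI) will be calculated to measure the magnitude of difference". This is a marginal RR.

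Section 13.5, Sensitivity analysis, then fits a logistic model with covariates. These are risk factors from the literature, plus baseline and perioperative variables that differ between arms at p < 0.10. The treatment term is described as dexmedetomidine use, which is not this trial's intervention. The plan notes that an OR may exaggerate the RR, which it names as its effect measure, and so "we will convert the OR into RR using the Zhang and Yu method". It does not say which control risk (P0) enters the formula, how the confidence interval is formed, or which covariates are used.

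The planning figures in section 4.2 are: "The incidence of postoperative delirium is about 14% in elderly patients who underwent laparoscopic surgery for colorectal cancer", and an assumption that "the incidence of postoperative delirium will be reduced by 1/3 in patients receiving EEG-guided care".

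**The concern.** The Zhang-Yu formula, RR = OR / ((1 − P0) + P0 × OR), is an identity when the OR is the unadjusted one. A multivariable logistic model gives an OR conditional on the covariates. The OR is non-collapsible: with a real effect and prognostic covariates, the conditional OR is further from 1 than the marginal OR, even under perfect balance. Combining it with an overall control risk leaves part of the overstatement that the conversion was meant to remove.

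A sensitivity analysis is read beside the primary result. Here, if the treatment works, the adjusted RR would tend to look better for an arithmetical reason and could be reported as an effect that strengthens after adjustment. The precision that covariate adjustment should bring would also not appear in the interval.

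**Working it through.** **Inputs from section 4.2.** Control risk P0 = 0.14; relative reduction one third, so P1 = 0.14 × 2/3 = 0.0933 and RR = 0.667; two-sided 0.05, power 80%; "the sample size required to detect the reduction is 742 patients per group". Allocation is 1:1 (section 5.1).

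**Assumptions not in the documents.** Covariate strength, expressed as the SD of a normal covariate score on the log-odds scale, with the matching AUC for delirium in the control arm. For intervals: P0 is the observed control incidence and the OR limits are transformed.

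**1. The plan's own figure.** With pooled variance and no continuity correction, mean risk is 0.1167 and n = [1.960 × √(2 × 0.1167 × 0.8833) + 0.842 × √(0.1204 + 0.0846)]² / 0.0467² = 742 per arm. The stated number reproduces.

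**2. No covariates.** OR = (0.0933/0.9067) / (0.14/0.86) = 0.632. Converted: 0.632 / (0.86 + 0.14 × 0.632) = 0.667, which is exact. At 742 per arm the transformed interval is 0.496 to 0.889, against 0.501 to 0.888 computed directly.

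**3. Prognostic baseline covariates.** Take logit(risk) = a + b × arm + s × Z, with Z standard normal. Solve a so that control risk averages 14%, and b so that intervention risk averages 9.33%. The true marginal RR is then 0.667 in every row.

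| s | AUC | Conditional OR | Converted RR | Apparent reduction |
|---|---|---|---|---|
| 0.5 | 0.64 | 0.625 | 0.659 | 34.1% |
| 1.0 | 0.75 | 0.601 | 0.636 | 36.4% |
| 1.5 | 0.83 | 0.564 | 0.601 | 39.9% |
| 2.0 | 0.88 | 0.520 | 0.558 | 44.2% |

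Example for s = 1: 0.601 / (0.86 + 0.14 × 0.601) = 0.636. With a control risk of 5% and the same values of s, the converted RRs are 0.664, 0.653, 0.630 and 0.598, so the shift shrinks with incidence.

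**4. Intervals.** Simulation with 742 per arm, eight baseline covariates and 3,000 trials per setting, true RR 0.667. Widths are on the log scale.

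| AUC | Zhang-Yu width | Standardised width | Crude width | Zhang-Yu vs standardised | Zhang-Yu coverage | Standardised coverage |
|---|---|---|---|---|---|---|
| 0.64 | 0.600 | 0.569 | 0.576 | 5% wider | 95.6% | 95.4% |
| 0.75 | 0.628 | 0.548 | 0.577 | 15% wider | 94.4% | 94.5% |
| 0.83 | 0.672 | 0.517 | 0.576 | 30% wider | 90.3% | 94.9% |

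At AUC 0.88, Zhang-Yu coverage was 85.3%. Standardised RRs were 0.66 to 0.67 throughout.

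**5. Test and null case.** Rejection rates for the two conversions agree (for example 0.845 and 0.845 at AUC 0.75). With a true RR of 1, the Zhang-Yu estimates average 0.998 to 1.002 and reject in 4.2% to 5.5% of trials.

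**The case against.** Zhang-Yu is a published conversion applied to one supporting analysis. Up to an AUC of about 0.75 the shift is at most 0.03 on the RR scale, well inside a primary interval of roughly 0.50 to 0.89, and coverage stays near 95%. Nothing in the documents shows that the covariates would be stronger. Section 3.2 excludes dementia, stroke and Parkinson's disease, and the case report form also excludes an MMSE of 23 or less, which removes some patients at high expected risk. This stands: a reader might infer that the adjusted and primary RRs cannot be compared at all, and the figures do not support that.

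A reader might also infer that this is the only robustness check on the primary result. It is the only analysis labelled a sensitivity analysis, but sections 3.4 and 13.3 also provide for per-protocol and as-treated populations.

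The most serious objection concerns direction. The plan admits perioperative variables, and section 7.2 collects propofol dose, burst suppression and SEF, which the intervention is meant to change. Adjusting for such mediators pulls the treatment OR towards 1. As an illustration, suppose a mediator is shifted 0.5 SD by treatment and carries 25% or 50% of the log-odds effect, with s between 0.5 and 1. The converted RR is then about 0.71 to 0.74, or 0.79 to 0.82. Standardising from that same model gives about 0.74 or 0.82, no closer to 0.667. This also stands. Overstatement is established only for covariates that treatment does not affect, and changing the conversion alone would not repair a model that contains mediators. It qualifies the direction and the fix; it does not make a conditional OR valid input to the formula.

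**Conclusion.** The point holds in a limited form. The planned conversion does not return the marginal RR that the plan names as its effect measure. With prognostic baseline covariates and a real benefit of one third, the adjusted RR would be about 0.66, 0.64 or 0.60 instead of 0.667 at an AUC of 0.64, 0.75 or 0.83. The distortion is small up to about 0.75 and material from about 0.83.

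These sizes rest on an assumed covariate strength and on section 4.2's 14% risk and one-third reduction. The width and coverage figures further assume a P0 and an interval method that the plan leaves open. A reader might take the wider interval to mean lost power or a changed conclusion; the matching rejection rates rule that out. There is no bias in the estimate under the null, and the primary test, its RR and the sample size are untouched. The correction is worth making because it is nearly free and prevents a misleading comparison.

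**What to change.** In section 13.5, Sensitivity analysis, replace the Zhang-Yu step with marginal standardisation (g-computation). From the logistic model, average the predicted risks with every patient set to SedLine-guided care and again with every patient set to usual care, take the ratio, and give a delta-method or bootstrap 95% interval. A modified Poisson model with robust standard errors is an acceptable alternative.

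State that the treatment term is the randomised arm, and restrict the covariates to a prespecified list of baseline variables. Standardisation recovers the marginal RR only if no covariate is affected by treatment.

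The cost is a few sentences in the SAP, agreement on the covariate list before unblinding, and a few lines of code. No new data are needed.
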